25.16 Systemic Reactions and Hypersensitivity Reactions

Please refer to local or institutional guidelines for monitoring relevant adverse events encompassing hypersensitivity, angioedema, anaphylaxis, acute anaphylactic shock and minor allergic episodes. Pre-medications will be permitted at the Investigator's discretion and will be appropriately documented.

25.17 Local infusion/injection site reactions (LI/ISR)

Injections may be associated with local reactions (e.g., swelling, induration, pain, bleeding, numbness). Local tolerability assessment is defined in this document.

25.18 Withdrawal Due to an Adverse Event

Any patient who experiences an adverse event may be withdrawn from the study at any time at the discretion of the Investigator. The patient will be monitored until the event has resolved or stabilized, until a determination of a cause related to the study product is made, or until the patient is referred to the care of a local health care professional. Additional reports must be provided when requested.

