- In the event that a patient develops any symptoms that could be possibly related to SARS-CoV-2 infection at home or out of the office, the patient must immediately test themselves using the SARS-CoV-2 Home Test Kit that was given to them at enrollment or go to a facility that can perform an EUA approved Breath Test for SARS-CoV-2 infection.
- In the event a positive test from the SARS-CoV-2 Home Test Kit or EUA approved Breath Test for SARS-CoV-2 infection is recorded, the patient must go to a qualified testing center and receive a SARS-COV-2 RNA by RT-PCR nasal swab test. These include LabCorp or Quest Diagnostics or a location that uses one of these two labs for the analysis (e.g., CVS).
- A positive SARS-COV-2 RNA by RT-PCR test must be sent to a qualified genomics laboratory (LabCorp or Quest Diagnostics) for detailed virus analysis
- In the event that a patient tests positive for SARS-CoV-2 infection by SARS-COV-2 RNA by RT-PCR, the patient should be instructed to contact their oncology center immediately
- In the event that a patient tests positive for SARS COV-2 RNA by RT-PCR, the patient must have blood drawn for serum concentration of AZD7442, RBD-IgG antibody level and T-cell analysis in the office approximately 10

days after the patient reported a positive test or in whatever timeframe is the acceptable protocol for a positive patient returning safely to the office of the Investigator.

- In the event that a patient develops a SARS-CoV-2 infection with symptoms, the patient should be immediately treated in accordance with Investigator judgement. Such treatment should include the current standard of care for symptomatic SARS-CoV-2 positive infection depending upon availability of immediate treatment. Such patient will be followed until day 360 of the study with all study procedures and assessments.
- Automatic request for patient medical records, pharmacy fill/refill data and medical insurance claims data for all patients for the 12 months post-baseline will be sent and forwarded to MediMergent for analysis.

[figure not shown]
Schedule of Activities:

	Screening/ Day 1 Baseline	Day 2	Day 30	Day 60	Day 90	Day 120	Day 150	Day 180	Day 181	Day 210	Day 240	Day 270	Day 300	Day 330	Day 360
Visit Window (Days)		+5	± 5	± 5	± 5	± 5	± 5	± 5	± 5	± 5	± 5	± 5	± 5	± 5	± 5
Informed Consent	X														
Authorization for Release of Health Info	X														
Inclusion/ Exclusion	X														
CBC including Platelet Count (if necessary)	X														

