25.7.2 Events that Meet the AE Definition

- Any event that occurred in the first 24 hours post AZD7442 administration
- Symptoms of SARS-CoV-2 infection
- Positive PCR-RT SARS-COV-2 test
- Any unplanned telehealth visit
- Any non-routine office visit

- Any ER/Urgent Care visit
- Signs, symptoms, or the clinical sequelae occurring in the first 24 hours post administration
- If the Investigator considers that there was a causal relationship between treatment with AZD7442 or protocol design/procedures and a patient's underlying disease progression, then this must be reported as an AE or SAE.
- Signs, symptoms, or the clinical sequelae of a suspected overdose of either study intervention or a concomitant medication. Overdose per se will be reported as an AE/SAE even if it was not associated with AE/SAE. Intentional drug overdose with possible suicidal/self-harming intent will be reported as an AE/SAE. Such overdoses will be reported regardless of sequelae.
- "Lack of efficacy" or "failure of expected pharmacological action" per se will not be reported as an AE or SAE. Such instances will be captured in the efficacy assessments. However, the signs, symptoms, and/or clinical sequelae resulting from lack of efficacy will be reported as AE or SAE if they fulfill the definition of an AE or SAE.

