25.8 Recording and Reporting Adverse Events

- For the purpose of processing and reporting adverse events, the study period is defined as that time period from signature of the informed consent form through the last visit of the study. AEs may be reported by the study participant (or, when appropriate, by a caregiver, surrogate, or the participant's legally authorized representative), the PI or the Study Coordinator.
- Reporting of non-serious adverse events will be limited to **ONLY** the following:
 - Any event reported by the patient on his/her follow-up survey in the first 24 hours post-administration of AZD7442
 - Any event reported by the patient on his/her follow-up survey that includes an unplanned telehealth visit, unscheduled physician office visit, ER/Urgent Care Visit
 - Any positive SARS-CoV-2 test by RT-PCR reported to the study site
 - Any symptoms of SARS-CoV-2 reported by the patient on any follow-up survey
 - If the Investigator considers that there was a causal relationship between treatment with AZD7442 or protocol design/procedures and a patient's underlying disease progression, then this must be reported as an AE or SAE.
- All AEs will be collected from baseline AZD7442 administration through day 360 post-baseline. SAEs will be collected from dose administration through the day 360 follow-up visit at the time points specified in the Schedule of Activities. However, any SAEs assessed as related to study participation (e.g., study intervention, protocol-mandated procedure, invasive tests or change in existing therapy) will be recorded from the time participant consents to participate in the study.
- Medical occurrences that begin before the start of study intervention but after obtaining Informed Consent will be recorded as Medical History/Current Medical Conditions not as AEs.
- All SAEs will be recorded and reported to the Sponsor or designee immediately and under no circumstance should this exceed 24 hours. The Investigator will submit any updated SAE data to the Sponsor or designee within 24 hours of it being available.
- Investigators are not obligated to actively seek information on AEs or SAEs after the conclusion of study participation. However, if the investigator learns of any SAE, including a death, at any time after a participant has been discharged from the study, and he/she

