- an important medical event that may not result in death, be life-threatening, or require hospitalization, but may jeopardize the patient and may require medical intervention to prevent the outcomes listed in this definition. Medical or scientific judgment should be exercised by the Investigator in deciding whether SAE reporting is appropriate in other situations such as significant medical events that may jeopardize the participant or may require medical or surgical intervention to prevent one of the other outcomes listed in the above definition. These events should usually be considered serious. Examples of such events include invasive or malignant cancers, intensive treatment for allergic bronchospasm,

blood dyscrasias, convulsions, or development of intervention dependency or intervention abuse.

- An adverse event that does not meet any of the criteria for seriousness listed above will be regarded as a non-serious adverse event.

25.13.2 Serious criteria pertaining to hospitalization should include the following:

- Any formal inpatient admission (even if less than 24 hours).
- Chronic or long-term inpatient admission: transfer within the hospital to an acute/intensive care inpatient unit (e.g., from the psychiatric wing to a medical floor, from a medical floor to the coronary care unit)

Serious criteria pertaining to hospitalization should NOT include the following:

- Emergency Room visits
- Outpatient/same-day/ambulatory procedures and observation/short- stay units
- Hospice facilities and Respite care (e.g., caregiver relief)
- Rehabilitation facilities, skilled nursing facilities, nursing homes, custodial care facilities.

The study period for the purposes of serious adverse event reporting is defined as the period from when the patient provides written informed consent to participate in the study until the patient completes the end of the follow-up period or withdraws from the study.

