25.19 Protocol Deviations Because of an Adverse Event

If a patient experiences an adverse event or medical emergency, deviations from the protocol may be allowed on a case-by-case basis. After stabilization and/or treatment for the emergency to protect patient safety has been administered, the investigator or other physician in attendance in such an emergency must contact the individual patient as soon as possible to discuss the circumstances of the emergency. The investigator will decide whether the patient should continue to participate in the study. Any protocol deviation related to adverse events should be noted in the patients' medical record along with the reason for such deviations.

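### Sections 25.18, 25.19 and 25.13.2 allow an adverse event, including breakthrough COVID-19, to end study follow-up and SAE collection, while 9.3 and 25.8 run both to Day 360; the protocol does not say which prevails

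*Protocol*

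**What the plan says.** **Passages that permit an early end**

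- Protocol 25.18: "Any patient who experiences an adverse event may be withdrawn from the study at any time at the discretion of the Investigator". The withdrawal is from the study, not only from treatment, and endpoint events are not excepted. The same section keeps the patient under observation for the triggering event, with three alternative end points: it resolves or stabilizes, a cause related to the product is determined, or the patient is handed over to local care.
- Protocol 25.19, on deviations after an adverse event or emergency: "The investigator will decide whether the patient should continue to participate in the study".
- Protocol 25.7.2 lists as adverse events "Symptoms of SARS-CoV-2 infection" and "Positive PCR-RT SARS-COV-2 test".
- Protocol 25.13.2, closing paragraph: the SAE reporting period runs "until the patient completes the end of the follow-up period or withdraws from the study".
- Protocol 25.8: "Investigators are not obligated to actively seek information on AEs or SAEs after the conclusion of study participation".

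**Passages that require follow-up to the end**

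- Protocol 9.3, on a patient with symptomatic infection: "Such patient will be followed until day 360 of the study with all study procedures and assessments".
- Protocol 25.8: "SAEs will be collected from dose administration through the day 360 follow-up visit at the time points specified in the Schedule of Activities".
- Protocol 9.3 also requests medical records, pharmacy and claims data on every patient for the 12 months after baseline.

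**The concern.** Symptomatic infection including related hospitalization and death, severe COVID-19 and time to first event are secondary endpoints (14.1). If the event that starts a patient's COVID-19 course may also end that patient's follow-up, the missing data are informative: they depend on having the outcome, and possibly on how ill the patient is. Ordinary missing-data methods do not repair this, because the patients who stay are not representative of those who leave.

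The primary endpoint is touched as well. It is serum concentration at Days 30 to 360 (13.1), and a withdrawn patient gives no further samples. The immunologic sub-study (16.1) relies on draws taken about 10 days after a positive test, which a patient withdrawn at the infection would not provide. Safety data are exposed in the same way, since 25.13.2 stops SAE reporting at withdrawal and the thrombotic and cardiac events of special interest (25.15) may occur later.

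**Working it through.** The protocol gives no figure to reproduce here. The check sets the sections side by side for one patient and asks what each requires.

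**1. A patient with symptomatic, RT-PCR-positive infection**

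| Question | 25.18, 25.19, 25.13.2 | 9.3, 25.8 |
|---|---|---|
| Does study follow-up continue? | At the investigator's discretion | Yes, to Day 360 with all procedures |
| Until when are SAEs collected? | Withdrawal, if it comes first | Day 360; withdrawal not mentioned |
| Is a later event actively sought? | Only the triggering event is monitored | Yes, as part of full follow-up |

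No cross-reference or order of precedence links the two columns, so a site can follow either one and cite the protocol.

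**2. A patient with any other adverse event.** The Day 360 rule in 9.3 is written for infection with symptoms. A patient with a thrombotic or cardiac event has no such protection, and 25.18 applies without a counterweight.

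**3. What is lost if 25.18 is applied**

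- Lost outright: later surveys and QoL assessments, later serum samples, and the post-infection AZD7442, RBD-IgG and T-cell draws if these have not yet been taken. None of these can be recovered from records or claims.
- Lost as reported SAEs: later events, by 25.13.2, except related ones that the investigator happens to learn of (25.8).
- Partly recoverable: later hospitalization or death, through monitoring of the triggering event (which handover to local care can end before the outcome is known) or through records and claims (if retrieval continues, which is not stated).
- Occasionally the infection itself: the ITT definition in 17.4 requires the Day 30 T-cell assay and at least one post-baseline RBD-IgG. A patient infected and withdrawn before these are drawn falls outside ITT, the population for the secondary analyses (14.2).

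**4. Scale.** The protocol gives neither an infection rate nor a withdrawal rate, so both are assumed here.

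- Infected patients: 1,500 × 5% = 75, up to 1,500 × 20% = 300.
- Withdrawn at infection, at 5% to 30% of those infected: 75 × 0.05 = 3.75, up to 300 × 0.30 = 90. That is about 4 to 90 patients.
- Share of later hospitalizations and deaths lost, if every such event in withdrawn patients is missed: with withdrawn fraction w and relative risk r in those withdrawn, rw / (1 − w + rw). For r = 1 this is w, so 5% to 30%. For r = 2 it is 2w / (1 + w): 0.10 / 1.05 = 9.5%, up to 0.60 / 1.30 = 46%.
- If sites follow 9.3, or records and claims are complete, the share is close to zero.

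The range is too wide to serve as an estimate. It shows only that the loss grows when sicker patients are the ones withdrawn.

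**The case against.** The strongest reply is that 9.3 is specific and mandatory, while 25.18 is a general, permissive safety clause. A careful site would apply 9.3 to a symptomatic infection, and nothing would be lost. That is a fair reading, but the protocol does not state it, and it does not help patients with other adverse events.

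Second, several routes still capture outcomes after withdrawal. Section 25.18 continues to monitor the triggering event. Section 25.7.5 follows SAEs to resolution or stabilization. Section 9.3 requests 12 months of records and claims, 17.5 accepts these as evidence of infection, and 20.1 lets the Clinical Events Committee grade severity from the health record. The infection that triggers withdrawal has usually been recorded by then. All of this stands. A reader might infer that infected patients simply lose their hospitalization and death follow-up; the documents do not support that. What they support is reliance on secondary routes whose continuation after withdrawal is not specified, together with the definite loss of surveys and blood samples.

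Third, 25.8 and 25.13.2 can be read together: a Day 360 window, cut short by withdrawal. That is possible, and it makes this part of the contradiction the weaker one. On that reading, however, SAE collection does stop at withdrawal, so the gap remains.

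**Conclusion.** The point holds as an unreconciled contradiction that permits outcome-related loss of follow-up. It affects secondary, sub-study and safety data directly, and the primary endpoint through missing later serum samples. The harm is conditional on sites applying 25.18 over 9.3, and its size cannot be derived from the protocol. It is worth correcting, but it does not undermine the design.

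Two further inferences are tempting and not supported.

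- A reader might conclude that the bias favours the study's own hypothesis of no difference between solid and hematologic patients. The no-difference hypothesis in 2.2 concerns serum concentration. For infection, 2.1 claims independence from type of cancer therapy and allows that cancer type may matter, and 23.7 expects less protection in hematologic malignancy.
- A reader might apply the 14.9% mortality quoted in 23.1 to an assumed number of infections and count lost deaths. That figure is background data on cancer patients with COVID-19. It does not describe vaccinated, AZD7442-treated patients selected for ECOG status below 2 and an expected survival of at least 12 months (8.1, 8.2). The count would also assume that no death is captured by any of the remaining routes.

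**What to change.** Reconcile 25.18, 25.19 and 25.13.2 with 9.3 and 25.8:

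1. In 25.18 and 25.19, state that an adverse event, including breakthrough infection, does not by itself end study follow-up and data collection. These continue to Day 360 unless the patient withdraws consent, dies or is lost to follow-up.
2. In 25.13.2, align the end of the SAE period with Day 360, as in 25.8.
3. In 9.3, state that the authorised records and claims retrieval for infection, hospitalization and death continues for patients who stop visits but have not withdrawn that authorisation (24.2).

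The wording should separate data collection from treatment. Decisions on AZD7442 treatment remain with the sponsor, and no treatment rule is proposed here.

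The cost is an edit to a few sections. The assessments are already in the Schedule of Activities for every patient. The downside is continued site contact with patients who would otherwise have been dropped.

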18.6 Investigator Responsibilities

The Investigator and any qualified designees are responsible for detecting, documenting, and reporting events that meet the definition of an AE or SAE and remain responsible for following up AEs that are serious, considered related to the

	
study intervention or the study, or that caused the participant to discontinue the study. Data on hospitalization or death should additionally be recorded on the Safety Report Form, for all relevant sections. The method of recording, evaluating, and assessing causality of AEs and SAEs and the procedures for completing and transmitting SAE reports are provided in the Safety Reporting section of this document.
 
18.7 MediMergent Pharmacovigilance
 
The MediMergent Pharmacovigilance team will be responsible for oversight of all safety data and for determining the expectedness of all SAEs, expedited reporting of individual cases, and safety updates to regulatory authorities and AstraZeneca.

19.0 Quality of Life Data
	
19.1 Quality-of-Life Evaluations
 
All Quality-of-Life data will be derived from questions in the baseline (Day 2) and follow-up QoL assessments. Each response will be given a numeric value and the sum of all responses will serve as the QoL “score” for a given patient at a given timepoint. The scoring will be determined such that the higher the score, the better the QoL. The comparison for all patients will use a change from baseline model. Scores at each time point for all patients for a given dose and cancer type will generate a mean, SD and SEM. The change from baseline at each post-baseline timepoint will be compared using two-tailed t-test comparison with $P < .05$ as significant. The mean change from baseline will be compared for all cancer patients treated with AZD7442 600 mg IM or IV and then sub-divided by comparisons between chemotherapy only, immunotherapy only, targeted therapy only and other/combination therapy only.

20.0 Adjudication: Clinical Events Committee (CEC)
	
20.1 Clinical Events Committee Functionality
 
An independent Clinical Events Committee (CEC) will be assembled to adjudicate/evaluate using a pre-specified adjudication operations manual, all clinical events data associated with SARS-COV-2 RNA by RT-PCR positive symptomatic SARS-CoV-2 infection including SARS-CoV-2 infection relatedness and/or impact on hospitalizations and deaths. In addition, the CEC will use the available clinical

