25.4 Investigator Responsibility

The Investigator and any qualified designees are responsible for detecting, documenting, and reporting events that meet the definition of an AE or SAE and remain responsible for following up AEs that are serious, considered related to the study intervention or the study, or that caused the participant to discontinue the study. Data on hospitalization or death should additionally be recorded on the Safety Report Form, for all relevant sections.

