25.7.5 Recording and Follow-up of AEs and SAEs

- When an AE/SAE occurs, it is the responsibility of the Investigator to review all documentation (e.g., hospital progress notes, laboratory, and diagnostics reports) related to the event. The Investigator will then record all relevant AE/SAE information. It is required for the Investigator to send photocopies or digital files of the participant's medical records to Sponsor in addition to completion of the required AE/SAE form. There may be instances when medical records for certain cases are requested by pharmacovigilance staff. In this case, all participant identifiers, with the exception of the participant number, will be redacted on the copies of the medical records before submission.
- The investigator will attempt to establish a diagnosis of the event based on signs, symptoms, and/or other clinical information. Whenever possible, the diagnosis (not the individual signs/symptoms) will be documented as the AE/SAE.
- After the initial AE/SAE report, the Investigator is required to proactively follow each participant at subsequent visits/contacts. All SAEs and non-serious AEs of special interest will be followed until the event is resolved, stabilized, otherwise explained, or the participant is lost to follow-up. Further information on follow-up procedures is given in this document.
- The Investigator is obligated to perform or arrange for the conduct of supplemental measurements and/or evaluations as medically indicated or as requested by pharmacovigilance to elucidate the nature and/or causality of the AE or SAE as fully as possible. This may include additional laboratory tests or investigations, histopathological examinations, or consultation with other health care professionals. If a participant dies during participation in the study or during a recognized follow-up period, the Investigator will provide sponsor with a copy of any post-mortem findings including histopathology. New or updated information will be recorded in the participant's medical record and submitted as supplemental information to the original report. The Investigator will submit any updated SAE data to the sponsor or designee within 24 hours of receipt of the information.

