25.7.7 Assessment of Causality

The Investigator is obligated to assess the relationship between study intervention and each occurrence of each AE/SAE.

- A "reasonable possibility" of a relationship conveys that there are facts, evidence, and/or arguments to suggest a causal relationship, rather than a relationship cannot be ruled out.
- The Investigator will use clinical judgment to determine the relationship.
- Alternative causes, such as underlying disease(s), concomitant therapy, and other risk factors, as well as the temporal relationship of the event to study intervention administration will be considered and investigated.
- The Investigator will also consult the Product Information (Package Insert), for marketed products, in his/her assessment.
- For each AE/SAE, the Investigator **must** document in the participant’s medical record that he/she has reviewed the AE/SAE and has provided an assessment of causality.
- There may be situations in which an SAE has occurred and the Investigator has minimal information to include in the initial report to sponsor. However, **it is very important that the Investigator always make an assessment of causality for every event before the initial transmission of the SAE data to Sponsor.**
- The Investigator may change his/her opinion of causality in light of follow-up information and send an SAE follow-up report with the updated causality assessment.
- The causality assessment is one of the criteria used when determining regulatory reporting requirements.

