25.12 Relationship of an Adverse Event to AZD7442

The relationship of an adverse event to AZD7442 is characterized as follows:

Definition of Adverse Event Relationship to AZD7442

Term	Definition	Clarification
No reasonable possibility (not related)	This category applies to those adverse events which, after careful consideration, are clearly due to extraneous causes (disease, environment, etc.) or to those adverse events, which, after careful medical consideration at the time they are evaluated, are judged to be unrelated to AZD7442.	The relationship of an adverse event to AZD7442 may be considered to have no reasonable possibility if it is clearly due to extraneous cause(s) such as: 
 • it does not follow a reasonable temporal sequence from the administration of AZD7442. • it could readily have been produced by the patient’s clinical state, environmental or toxic factors, or other modes of therapy administered to the patient.
Reasonable possibility (related)	This category applies to those adverse events for which there is evidence to suggest a causal relationship between the drug and the adverse even after careful medical consideration at the time they are evaluated, a connection with AZD7442 administration was felt with a high degree of certainty to be related to AZD7442.	The relationship of an adverse event to AZD7442 may be considered reasonable possibility related if: 
 • it follows a reasonable temporal sequence from administration of AZD7442 and/or • conveys in general that there are facts (evidence) or arguments to suggest a causal relationship.

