25.15 Adverse Events of Special Interest

Adverse events of special interest are defined in the study protocol as relevant known toxicities as a result of signals observed from previous studies in the non-clinical programs of AZD7442. These will be updated during the course of the study based on accumulating safety data. AESI include:

- Reactions including hypersensitivity reactions occurring on same day as vaccination
- Local injection site reactions
- Coronary Ischemia
- Myocardial Infarction
- Congestive Heart Failure
- Thrombotic events-coronary, cerebral, abdominal, pulmonary or peripheral vascular

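### Section 25.18 lets monitoring after withdrawal for an adverse event stop because the event is attributed to AZD7442, against the direction of sections 18.6 and 25.4

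*Protocol*

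**What the plan says.** Section 25.18 allows the investigator to withdraw a patient who has an adverse event and then gives three alternative points at which monitoring ends, joined by 'or':

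- the event has resolved or stabilized;
- monitoring runs "until a determination of a cause related to the study product is made";
- the patient has been referred to a local health care professional.

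Sections 18.6 and 25.4, in the same words, keep the investigator responsible for following up events that are serious, or "considered related to the study intervention or the study, or that caused the participant to discontinue the study".

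Three other sections bear on this:

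- Section 25.7.5 says that after the initial report "the Investigator is required to proactively follow each participant at subsequent visits/contacts". It gives explicit end points for serious events and non-serious events of special interest: resolution, stabilization, another explanation, or loss to follow-up.
- Section 25.7.7 makes the investigator "obligated to assess the relationship between study intervention and each occurrence of each AE/SAE".
- Section 25.12 offers two outcomes for that assessment, related and not related.

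**The concern.** Attribution to the study drug is normally a reason to watch an open event more closely. Sections 18.6 and 25.4 treat it that way, and section 25.18 does the reverse. It is also the section that deals specifically with monitoring after withdrawal for an adverse event, so a site is likely to consult it first. A site that applied it literally could stop monitoring a withdrawn patient whose event is still active, on the ground that AZD7442 caused it. The course and outcome of that event would then be less well documented. What is at stake is the completeness of safety follow-up in a few patients, not any efficacy or pharmacokinetic result.

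**Working it through.** The plan states no figure on this point, so the check is a comparison of the texts.

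**Step 1: when the disputed clause operates.** Resolution or stabilization is already its own alternative in 25.18, and so is referral. The disputed clause therefore changes the outcome only when the event is neither resolved nor stabilized and the patient has not been referred.

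**Step 2: apply 25.18 to such an event under both causality outcomes of 25.12.**

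| Causality judgment | Literal reading of the clause | Softer reading (until causality is settled) |
|---|---|---|
| Related | monitoring may end | monitoring may end |
| Not related | monitoring continues | monitoring may end |

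On the literal reading, related events are treated less protectively than unrelated ones. The softer reading removes that asymmetry but still ends monitoring on a finding of relatedness. Because 25.7.7 requires a causality assessment for every event, the softer reading could also end monitoring as soon as that assessment is made.

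**Step 3: apply 18.6 and 25.4 to the same patient.** These sections name three grounds for continuing responsibility: serious, related, or the cause of discontinuation. A related, non-serious event that led to withdrawal meets the second and third. The fact that ends monitoring under 25.18 is a ground for follow-up here.

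**Step 4: remove the cases that another rule covers.** Section 25.7.5 sets end points for all serious events and for non-serious events of special interest, and attribution to study product is not among them. The special-interest list in 25.15 includes "Local injection site reactions", same-day reactions including hypersensitivity, coronary ischemia, myocardial infarction, congestive heart failure and thrombotic events. Many plausible drug reactions are therefore covered.

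**Step 5: what remains.** The exposed event is non-serious, not of special interest, judged related, the reason for withdrawal, neither resolved nor stabilized, and not referred. The protocol gives no withdrawal rate for adverse events, so this group cannot be turned into a number of patients.

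**The case against.** The strongest reply is that the two rules are not strictly incompatible. Sections 18.6 and 25.4 say which events remain the investigator's responsibility and set no end point. Section 25.18 supplies end points, and its referral alternative also releases the site from an unresolved, related event without anyone calling that a contradiction. This stands in part: having a stopping rule is not the problem. Using relatedness as the stopping reason is, because the other two sections give that same fact as a reason to continue.

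A second reply is that 25.7.5 protects these patients anyway. It does so for serious and special-interest events. For the rest it imposes a general duty to follow at later visits or contacts, states no end point, and does not say what those contacts are once a patient has been withdrawn.

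A third reply is that the clause is an obvious slip for 'unrelated'. That is likely, since the corrected word would fit the alternative-explanation end point of 25.7.5. It supports correcting the text.

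Two stronger readings are tempting and are not supported:

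- A reader might take AZD7442-caused cancer progression as the main example, because section 25.8 makes progression reportable when the investigator sees a "causal relationship between treatment with AZD7442 or protocol design/procedures" and that progression. But sections 18.4 and 25.3 list worsening of the underlying cancer among the likely serious events, and 25.8 allows such progression to be reported as serious. Much of it would then be governed by 25.7.5.
- A reader might count the routes by which monitoring can end for related and unrelated events and treat the difference as a measure of harm. Counting clauses measures neither patients nor follow-up time.

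The reportable classes in 25.8 also do not limit the problem. Section 25.18 covers any adverse event that leads to withdrawal, whether or not it falls in one of those classes.

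**Conclusion.** The point holds as a minor drafting error in an operative safety rule. As worded, 25.18 allows attribution of an open event to AZD7442 to end monitoring by itself, while 18.6 and 25.4 make relatedness and having caused discontinuation grounds for continued follow-up. The conclusion rests on reading the three alternatives in 25.18 as disjunctive, which their wording requires. It does not depend on choosing between the literal and softer readings of the clause.

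The effect is confined to the narrow group in step 5 of the working. A reader might infer that the protocol releases sites from following serious drug-related harm generally. It does not, because 25.7.5 sets separate end points for serious and special-interest events. No endpoint, analysis, power or sample size is affected.

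**What to change.** In the next amendment, remove attribution to AZD7442 as a stopping condition in 25.18. Either of two edits does this:

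1. Change 'related' to 'unrelated' in the disputed clause.
2. Replace the clause with the alternative-explanation end point of 25.7.5, making clear that attribution to AZD7442 does not count as such an explanation.

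Under either edit, an event judged related to AZD7442 is monitored until it resolves or stabilizes or the patient is referred. Add cross-references to 18.6, 25.4 and 25.7.5.

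Simply deleting the clause would also remove the inversion. It would, however, leave 25.18 with no end point for events explained by another cause, and so stricter on that point for a non-serious event than 25.7.5 is for a serious one. Either edit above fits the rest of the protocol better.

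The cost is one changed clause and the cross-references. No scheduled visit or assessment changes. Sites may need a few extra contacts for related events that are unresolved and not yet referred.
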